7.0 CLINICAL MANAGEMENT ISSUES

Criteria for **participant** management, dose interruptions, modifications and discontinuation of treatment will be mandated only for toxicities attributable to sirolimus.

The grading system for drug toxicities is located in the Division of AIDS Table for Grading the Severity of Adult and Pediatric Adverse Events, **Version 2.0, November 2014**, which can be found on the DAIDS RSC Web site: <http://rsc.tech-res.com/safetyandpharmacovigilance/>.

NOTE: The protocol core team must be notified by e-mail at [contact] within 48 hours regarding toxicities that result in a change in study treatment (including permanent discontinuation) during the study-defined 20-week treatment period.

7.1 Toxicity

7.1.1 Grade 1 or 2 Toxicity

Participants who develop a Grade 1 or 2 AE or toxicity felt to be related to study drug may continue study treatment. If a **participant** chooses to discontinue study treatment, the site should notify the protocol core team at [contact] within 48 hours and follow the **participant** on study/off study treatment.

7.1.2 Grade 3 Toxicity

- If the investigator has compelling evidence that the AE has NOT been caused by the study drug, dosing may continue. **Participants** who develop a Grade 3 AE or toxicity, except as stated in the following sections, should have sirolimus

withheld, and the A5337 core team consulted. The **participant** should be reevaluated weekly until the AE returns to Grade ≤ 2 , at which time the study drug may be reintroduced at the discretion of the investigator or according to standard practice.

- If the same Grade 3 AE recurs within 4 weeks, the study drug must be permanently discontinued if the investigator considers the AE related to study drug. However, if the same Grade 3 AE recurs after 4 weeks, the management scheme outlined above may be repeated.
- **Participants** experiencing Grade 3 AEs requiring permanent discontinuation of study drug should be followed weekly until resolution of the AE and should be encouraged to complete the early discontinuation evaluations and continue in on-study follow-up.

7.1.3 Grade 4 Toxicity

- **Participants** who develop a Grade 4 symptomatic AE or toxicity will have study drug permanently discontinued and should notify the protocol core team at [contact] within 48 hours. **Participants** experiencing Grade 4 AEs requiring permanent discontinuation of study drug should be followed weekly until resolution of the AE or return to baseline and encouraged to complete the early discontinuation evaluations and continue on-study follow-up.
- **Participants** with Grade 4 asymptomatic laboratory abnormalities may continue study drug if the investigator has compelling evidence that the toxicity is NOT related to the study drug.

7.1.4 CD4+ Decrease

Study drug will be discontinued in **participants** who exhibit CD4+ cell count decrease to <300 cells/mm³ or decreases $>50\%$ from study entry value on two consecutive assessments.

7.1.5 Detectable HIV-1 RNA

Study drug will be discontinued in **participants** who have HIV-1 RNA >200 copies/mL on two consecutive assessments.

7.1.6 Detectable EBV in Blood

Sirolimus will be discontinued if EBV DNA is detected.

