- 4.2.12 History of congestive heart failure as defined by physician documentation in the medical record at any time prior to screening that required medication for heart failure or that required medical management within 2 years prior to study entry.

- 4.2.13 Detectable Epstein-Barr virus (EBV) in blood by polymerase chain reaction (PCR) within 90 days prior to study entry at any US laboratory that has a CLIA certification or its equivalent.

- 4.2.14 Active infection other than HIV that required receipt of systemic antibiotic therapy by intravenous infusion within 90 days prior to study entry.

- 4.2.15 Life-threatening fungal infection that in the opinion of the site investigator requires treatment within 48 weeks prior to study entry.
- 4.2.16 Herpes-zoster or varicella-zoster viral infection requiring treatment within 90 days prior to study entry or currently on suppressive therapy.
- 4.2.17 History of major hypersensitivity reaction to macrolide drugs including angioedema, anaphylaxis, drug-induced dermatitis or hypersensitivity vasculitis.
- 4.2.18 Currently pregnant or breastfeeding, or planning to become pregnant prior to or during the study.
- 4.2.19 Use of immunomodulators (e.g., interleukins, interferons and cyclosporine), HIV vaccine, systemic cytotoxic chemotherapy, or investigational therapy within 90 days prior to study entry.
- 4.2.20 Active drug or alcohol use or dependence that in the opinion of the site investigator would interfere with adherence to study requirements.
- 4.2.21 Vaccination (e.g., pneumococcal polysaccharide/influenza vaccine) within 14 days prior to study entry.

NOTE: If **participants** receive influenza vaccination for routine clinical care during or prior to the screening visit, they may be rescreened 14 days after vaccination.

- 4.2.22 On a PI-based ART or cobicistat-boosted regimen within 90 days prior to study entry or plans to change to a PI-based or cobicistat-boosted regimen during the study.

NOTE: Prior PI-based or cobicistat-boosted regimens are allowed.

- 4.2.23 Anal or perianal administration of anti-HPV therapies (e.g., imiquimod, 5FU, veregen) for 90 days prior to study entry or plans to initiate anti-HPV therapies during the study.

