6.0 CLINICAL AND LABORATORY EVALUATIONS

6.1 Schedule of Events

Evaluation	Screening	Entry	Sirolimus Initiation	Post-Entry Evaluations								Premature Treatment or Study Discontinuation	Confirmation of CD4 Decrease	Confirmation of Virologic Failure
	Week	0	12	13	14	16	20	24	32	44				
Days Post-Sirolimus Initiation			0	4	11	28	56	84	140	224				
Window	Within 60 days prior to entry		±1 week	±1 day (same days as PK)			±1 week (same days as PK)			±2 weeks				
Documentation of HIV	X													
Medical & Medication History	X	X												
Clinical Assessment	X	X	X	X	X	X	X	X	X	X	X			
Complete Physical Exam	X													
Targeted Physical Exam		X	X		X	X	X	X	X		X	X	X	
Hematology	X	X	X	X	X	X	X	X	X	X	X			
Liver Function Tests	X	X	X	X	X	X	X	X	X	X	X			
Blood Chemistry	X	X	X	X	X	X	X	X	X	X	X			
Calculated Creatinine Clearance	X	X	X	X	X	X	X	X	X	X	X			
Urinalysis	X		X		X	X	X							
Pregnancy Testing	X	X	X	if indicated										
Hepatitis Serology (see section 6.3.5)	X													
Assessment for Reactivation of Latent EBV	X						X	X	X	X	X			
CD4+/CD8+	X	X	X	X	X	X	X	X	X	X	X			

Evaluation	Screening	Entry	Sirolimus Initiation	Post-Entry Evaluations								Premature Treatment or Study Discontinuation	Confirmation of CD4 Decrease	Confirmation of Virologic Failure	
	Week	0	12	13	14	16	20	24	32	44					
Days Post-Sirolimus Initiation			0	4	11	28	56	84	140	224					
Window	Within 60 days prior to entry			±1 week	±1 day (same days as PK)			±1 week (same days as PK)			±2 weeks				
Cryopreserved PBMCs for HIV-1 Gag-specific CD8+ and CD4+ cell Immunity		X	X	X		X		X	X	X		X			
Stored Plasma for Inflammatory and Coagulation Markers		X	X	X		X		X	X	X		X			
Cryopreserved PBMCs for Markers of T-cell Activation and Proliferation		X	X	X		X		X	X	X		X			
Cryopreserved PBMCs for Exploratory Studies		X	X	X		X	X	X	X	X		X			
Stored Plasma for Antibody Quantitation		X	X	X				X	X	X		X			
Plasma HIV-1 RNA	X	X	X			X	X	X	X	X		X			X
HIV-1 Drug Resistance Genotyping (see section 6.3.7)															X
Cryopreserved PBMCs for Inducible RNA Assay			X					X	X	X					
Cryopreserved PBMCs for Cell-Associated RNA and DNA		X	X	X		X		X	X	X		X			
Stored Plasma for Residual Viremia by Single-Copy RNA Assay		X	X	X		X		X	X	X		X			
Stored Whole Blood for Gene Expression Assay			X	X		X		X	X	X					
Stored Plasma and PBMCs for Future Unspecified Testing		X	X	X		X		X	X	X		X			
Tuberculosis Test (see section 6.3.11)	X														
Chest Radiograph	X														
Anal Swabs/Anal Pap Test			X						X						

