6.2 Timing of Evaluations

6.2.1 Screening Evaluations

Screening evaluations must occur before any study medications, treatments or interventions.

Screening evaluations to determine eligibility must be completed within 60 days prior to study entry, unless otherwise specified.

In addition to data being collected on **participants** who enroll into the study, demographic, clinical, and laboratory data on screening failures will be captured in a Screening Failure Results form and entered into the ACTG database.

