6.2.2 Entry Evaluations

Entry evaluations, including collection of all entry specimens, must occur at least 48 hours after screening evaluations, unless otherwise specified, and prior to the **participant's** starting any study medications, treatments, or interventions.

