6.2.3 Post-Entry Evaluations

Prior to starting sirolimus, laboratory measurements from the week 12 visit must be assessed to ensure that the criteria detailed in section 4.1.6 and 4.1.10 continue to be satisfied, as well as week 12 CD4+ cell count >300 cells/mm³. If any criterion is not satisfied, the study team should be promptly contacted and sirolimus should not be started. In addition, concomitant medications must be re-assessed at the week 12 visit to ensure that the **participant** has not received any prohibited medications since study entry. If so, the study team should be promptly contacted and sirolimus should not be started.

Participants must begin study treatment within 72 hours after receipt of results from the study week 12 evaluations.

Site staff is encouraged to contact **participants** at least 14 days prior to scheduled study visits (not PK-only visits) to remind **participants** not to receive any vaccinations prior to their visit. A reminder can also be given that prohibited medications are not allowed at any time while on study.

For stored samples, all sites must have established procedures for regular reconciliation and verification of specimens, which must be followed throughout the study per the Lab Processing Chart (LPC). Collection of sample aliquots is of particular importance at the pre-sirolimus time points (entry and week 12) and at the study week 32 time point. In the event that the required volume or number of sample aliquots is not obtained at any time point, designated site clinic and/or lab staff must immediately inform the study team, who will provide guidance on how to respond to the problem.

In addition to following this guidance from the study team, designated site clinic and lab staff will work together to document the problem, take appropriate corrective and preventive action, and document all action taken. Reconciliation must be performed for all specimen types that are received by the laboratory and stored in the LDMS.

For other evaluations, if an evaluation is not completed at a scheduled visit, effort should be made to obtain the evaluation as soon as possible. If unsuccessful, complete the evaluation at the next study visit if not already included as part of the regularly scheduled visit.

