NOTE: Sites must contact the A5337 core team prior to the scheduled week 12 visit, ideally at least 2 weeks before, for confirmation that a **participant** may begin study treatment based on availability of stored samples at study entry. This confirmation must be documented in the source document prior to initiation of sirolimus.

On-Treatment Evaluations (weeks 12 through 32)

The window for week 12 is ± 1 week and for weeks 13 through 16 is ± 1 day as visits will be timed with the PK evaluations. The window for weeks 20 through 32 is ± 1 week.

NOTE: Starting with week 12, days should be counted from the first date of actual sirolimus dosing. Day 0 is the date of the first dose of sirolimus.

Post-Treatment Evaluations (week 44)

The week 44 visit is the final study visit. The window for the week 44 visit is ± 2 weeks.

Event Driven Evaluations

Confirmation visit to confirm CD4+ cell count <300 cells/mm 3 or $>50\%$ CD4+ decrease from study entry value or HIV-1 RNA >200 copies/mL (see sections 7.1.4 and 7.1.5) should be scheduled within 1 week of receipt of the abnormal lab value. If confirmed CD4+ cell count <300 cells/mm 3 or $>50\%$ CD4+ decrease from study entry value or HIV-1 RNA >200 copies/mL, the study team should be promptly contacted and sirolimus should not be started or should be stopped if already started.

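### The only scheduled blood EBV PCR before the first sirolimus dose is the screening test, about 11 to 22 weeks old by then, and the week-12 pre-dose check does not repeat it

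*Protocol*

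**What the plan says.** Protocol section 4.2.13 excludes anyone with "Detectable Epstein-Barr virus (EBV) in blood by polymerase chain reaction (PCR) within 90 days prior to study entry". The anchor is study entry, which opens a 12-week lead-in without sirolimus.

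In the section 6.1 schedule, the row "Assessment for Reactivation of Latent EBV" is marked at screening, at weeks 20, 24, 32 and 44, and at premature discontinuation. Entry and weeks 12, 13, 14 and 16 are blank. Section 6.3.5 defines the test as a quantitative PCR on serum or plasma in a CLIA-certified or equivalent laboratory.

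Before the first dose, section 6.2.3 requires that week-12 laboratory results "must be assessed to ensure that the criteria detailed in section 4.1.6 and 4.1.10 continue to be satisfied". It adds a CD4+ count above 300 cells/mm³ and a review of prohibited medications. For a confirmed CD4+ fall or a confirmed HIV-1 RNA above 200 copies/mL, the same section says "sirolimus should not be started or should be stopped if already started". EBV appears in neither place.

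On treatment, section 7.1.6 reads: "Sirolimus will be discontinued if EBV DNA is detected". It asks for no confirmatory test and no comparison with a baseline value.

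The clarification memoranda in the protocol file, as far as they are shown, leave all of this unchanged.

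**The concern.** Sirolimus is an immunosuppressant, and section 2.1.5 lists activation of latent EBV and possible lymphoma among its risks. The protocol takes this seriously enough to exclude on EBV at screening and to stop the drug on a single detection. It does not look again just before the first dose, when a positive result could still keep the participant off the drug.

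Two things are at stake. The first is individual safety: a person who turns positive in the lead-in could be dosed with detectable EBV and, if it persists, would not be found by a scheduled test until week 20. The second is attribution. Section 9.5 asks the core team to judge whether events are related to study treatment, and counts discontinuations attributed to the drug towards a 25% trigger for committee review. With no planned pre-dose value close to the start of treatment, a week-20 positive that began in the lead-in looks the same as reactivation on drug.

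**Working it through.** The documents give no figure for the age of the EBV result at dosing, so there is none to reproduce. It follows from the visit windows.

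**Inputs**
- Screening to entry, upper limit: 60 days. Section 6.2.1: "Screening evaluations to determine eligibility must be completed within 60 days prior to study entry, unless otherwise specified".
- Screening to entry, lower limit: 2 days. Section 6.2.2 says entry evaluations "must occur at least 48 hours after screening evaluations".
- Entry to the week-12 visit: 84 ± 7 days, that is 77 to 91 (sections 6.1 and 6.2.3).
- Week-12 results to first dose: 0 to 3 days. Section 6.2.3 says participants "must begin study treatment within 72 hours after receipt of results from the study week 12 evaluations". Laboratory turnaround is not stated and is set to zero.
- First on-drug EBV test: day 56 ± 7 after the first dose, as the section 6.1 table reads.

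**Age of the EBV result at first dose** = (screening to entry) + (entry to week 12) + (results to dose)
- Minimum: 2 + 77 + 0 = 79 days; 79/7 = 11.3 weeks.
- Maximum, 60-day window: 60 + 91 + 3 = 154 days; 154/7 = 22.0 weeks.
- Maximum if the 90-day limit in section 4.2.13 is taken as the exception that section 6.2.1 allows: 90 + 91 + 3 = 184 days; 184/7 = 26.3 weeks.

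**Interval on drug before the next scheduled test**
- 56 − 7 = 49 days to 56 + 7 = 63 days, which is 49/140 = 35% to 63/140 = 45% of the 20-week course.
- From the screening test to the next scheduled test: 79 + 49 = 128 days (18.3 weeks) to 154 + 63 = 217 days (31.0 weeks), under the 60-day window.

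**EBV beside the other measures that can stop or hold sirolimus**

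| Measure | On-drug rule | Can week 12 block the first dose? |
|---|---|---|
| CD4+ count | 7.1.4, two consecutive values | Yes, 6.2.3 |
| HIV-1 RNA | 7.1.5, two consecutive values | Yes, 6.2.3 |
| AST, ALT | 7.2.1 | Yes, through 4.1.10 |
| Neutrophils, platelets | 7.2.3 | Yes, through 4.1.10 |
| Creatinine clearance, urine protein ratio | 7.2.4 | Yes, through 4.1.10 |
| Triglycerides, LDL | 7.2.5 with 7.1.2 and 7.1.3 | Yes, through 4.1.10 |
| Pregnancy | 7.4 and 8.1 | Yes, through 4.1.6 |
| EBV DNA | 7.1.6, one detection | No; not measured at week 12 |

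Total cholesterol, also named in 7.2.5, is drawn at week 12 but has no limit in 4.1.10. Hepatitis serology, the TB test and the chest x-ray are also screening-only, but none has an on-drug stop rule of its own. EBV is the one laboratory measure in the table that has a stop rule and no week-12 measurement.

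**The case against.** The strongest reply is that this is a choice of monitoring frequency in a protected population. EBV-positive people are excluded at screening. So are those with lymphoproliferative disease or most malignancies. CD4+ count must be at least 350 with 24 months of suppression, immunomodulators are barred from entry, and EBV is tested repeatedly on drug. Nothing in the documents shows that EBV is likely to emerge in a drug-free lead-in. All of this limits the concern, but none of it is an EBV result at dosing.

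A reader might go further than the documents allow in four ways.

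- *That someone positive at week 12 already meets a mandatory stop criterion.* Section 7.0 mandates discontinuation only for toxicities attributable to sirolimus, and virus present before the first dose is not that. Section 7.1.6 carries no such condition, so the reading is open. The supportable statement is that such a person could start with detectable EBV.
- *That the cause of a week-20 positive could never be settled.* Section 6.1 stores plasma at entry and week 12 for unspecified testing, and the PCR runs on plasma. A retrospective test would be possible, though it is not planned, section 6.3.10 makes storage subject to blood-volume limits, and it would protect no one before dosing. The oral swabs at those visits serve an exploratory outcome and are not blood.
- *That a number of affected participants can be given.* The documents contain no conversion or persistence rate.
- *That the timing of the first on-drug test is certain.* The extracted table has some column doubt: the urinalysis marks, for example, sit differently from those in SAP Table 1, which has no EBV row to check against. A shift of one column would move the week-20 test and the 49 to 63 days. It would take a shift of four columns to put a mark at week 12.

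**Conclusion.** The point holds as a specific safety gap by the protocol's own logic. It is not a contradiction in the plan: an undetectable EBV result is on file at dosing, but it predates the whole lead-in.

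Its documented size is the age of that result: 79 to 154 days (11.3 to 22.0 weeks) with the 60-day window and no laboratory turnaround, or up to 184 days if a result from the 90-day look-back is accepted. Exposure before the next scheduled test is about 8 weeks, conditional on the table columns being read correctly. How many of the 30 participants would be affected is unknown and could be none. The attribution problem is real but partial, because stored week-12 plasma may exist. Nothing in the documents supports a claim of material effect on the efficacy results.

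**What to change.** Three edits to the protocol:

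1. Section 6.1: mark the blood EBV PCR in the week-12 column.
2. Section 6.2.3: add an undetectable week-12 EBV PCR to the results that must be reviewed before the first dose.
3. Section 5.1: this section counts the 72 hours to treatment start from the week-12 (day 0) evaluations, while section 6.2.3 counts from receipt of their results. Change section 5.1 to match section 6.2.3. Otherwise a site waiting for the PCR could comply with one section and breach the other.

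The cost is about 30 extra clinical PCRs at a visit that already draws blood, and possibly a short wait for the result; the documents give no turnaround time. Anyone found positive would not start and would be replaced under section 6.2.4, including a person whose positive was transient. By the arithmetic above, a replacement needs 79 to 154 days from screening to first dose. No new visit is needed.

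For anyone already dosed who has a positive on-drug test, testing stored week-12 plasma, where it exists, would recover part of the attribution information.

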7.1.7 CMV viremia

CMV viremia without evidence of end-organ involvement will not require study drug termination.

7.2 Management of Specific Toxicities

7.2.1 Hepatotoxicity

Liver function test (LFT) monitoring will be performed as detailed in section 6.0. In the event that there is an increase in ALT or AST to $>5 \times$ ULN, sirolimus will be stopped and LFT blood testing will be repeated every 2 weeks until the values have returned to normal range.

7.2.2 Pulmonary Toxicity

All potential **participants** will have a chest x-ray and pulse oximetry measured prior to starting sirolimus therapy. Respiratory symptoms such as shortness of breath or coughing will be monitored at each study visit. If **participants** develop serious unexplained cough or shortness of breath suggestive of interstitial lung disease, they will be told not to take the next dose of study medication. An additional evaluation should be performed at the discretion of the site investigator, which may include pulse oximetry, physical examination, imaging including chest x-ray, chest computed tomography (CT scan) and possible referral to a pulmonologist or other specialist.

NOTE: Sirolimus will be held for Grade 2 dyspnea. At the discretion of the site investigator, in consultation with the protocol team, study treatment may be withheld or discontinued for Grade 1 pulmonary toxicity. Once the dyspnea has resolved sirolimus may be restarted with caution. If dyspnea recurs, sirolimus must be discontinued.

7.2.3 Myelosuppression

Sirolimus will be held for neutrophil toxicity (ANC $<1000 \text{ cells}/\mu\text{L}$) and thrombocytopenia ($<100,000/\text{mm}^3$) until repeat testing confirms these results. At the discretion of the site investigator and in consultation with the protocol team, study treatment may be permanently discontinued.

7.2.4 Nephrotoxicity

Any **participant** with a calculated CrCl $<50 \text{ mL}/\text{min}$ or a reduction in CrCl by 30% or more should have the value confirmed within 7 days. Sirolimus will be discontinued if confirmed calculated CrCl decreases by $>30\%$ after initiation of treatment or falls below $50 \text{ mL}/\text{min}/1.73 \text{ m}^2$.

Urine protein to creatinine ratios will also be checked per the SOE. Sirolimus will be discontinued if the ratio is $>1 \text{ g/g}$.

